### 8.2.1 Treatment Logs/Bleeding Verification

Treatment logs are commonly used for hemophilia participants for documentation of their home treatment. Home treatment and bleeding information are the key variables for evaluation of effectiveness. Study-specific treatment logs will be provided in the national language. The system for this study will be an eDiary since this allows for an interactive, record-stamp date and time of fulfillment and facilitates the clarification of data with the site as well as the data cleaning process. Participants will be provided access to the eDiary for the entire study. At the Baseline Visit, participants (and their parent[s] or legal guardian) will be trained in the use of the eDiary. These logs will be used to document the treatment data and bleeding episodes by the participants, and the data will be verified for accuracy and completion by the investigator or delegate during regularly scheduled interactions with the participant. Thus, the eDiary will be considered the source for these data. In the event a participant does not have internet access, alternative means of diary completion will be provided.

For each infusion of Jivi, information must be recorded in the diary as follows:

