#### 4.3.2.1 Patient Reported Outcomes

PRO data will be collected in an eDiary form made available for Baseline (HAEM-A-QoL or HAEM-QoL [adult or kids], EQ-5D-5L, WPAI+CIQ:HS, TSQM-9 [baseline]), Month 3 (EQ-5D-5L only), and EOS (HAEM-A-QoL or HAEM-QoL, PGI-C, EQ-5D-5L, WPAI+CIQ:HS, TSQM-9) visits. Frequency summaries will be presented by visit and continuous variables will be described by absolute value and as change from baseline. Missing data will not be imputed.

- Haemophilia Quality of Life Questionnaire transformed scale scores (%) will be presented separately for participants ages  $\geq 17$  years and for those age 12-16.
  - *HAEM-A-QoL (adult)* has 46 questions in 10 groups
  - *HAEMO-QoL KIDS (ages below 16)* short form has 35 questions

Steps to calculate total scoreii:

- Assorting: Assign the numbers to each question response
- Recoding (HAEM-A-QoL): Numeric scores will be assigned to each item so that highest score is most impaired: 1= never, 2=seldom, 3=sometimes, 4=often, 5=all the time for negatively worded items or 1=all the time, 2=often, 3=sometimes, 4=seldom, 5= never for positively worded items.
  1. Physical Health, 5 questions, no recoding is needed
  2. Feeling, 4 questions, no recoding is needed
  3. View of yourself, 5 questions, #2 and #5 must be recoded
  4. Sports and Leisure, 5 questions, #3 must be recoded
  5. Work and School, 4 questions, #1 and #2 must be recoded
  6. Dealing with Hemophilia, 3 questions, #1, #2, #3 must be recoded
  7. Treatment, 8 questions, #8 must be recoded
  8. Future, 5 questions, #2 must be recoded
  9. Family Planning, no recoding is needed
  10. Partnership and Sexuality, 3 questions, no recoding is needed
- Recoding (HAEMO-QoL KIDS): Total Score, 35 questions, #11, #12, #17, #18, #19, #27, #28, #29, #30, #31, #32 must be recoded

- Summing up the total score for each HAEM-A-QoL sub-scale and for the HAEM-A-QoL and HAEMO-QoL KIDS total scores
- Transferring a raw score to a transformed scale score between 0 and 100. The raw score range lies between the lowest possible (number of items (n) x 1) and highest possible (number of items(n) x 5) value of the respective scale. Missing items will be omitted from the raw score and also from the n used to calculate range.
- Patient's Global Impression of Change (PGI-C);

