  - Scores will be presented as a frequency table and median response where 3 = very much improved, 0 = no change, and -3 = very much worse. The proportion and 95% CI of participants with any improved score at EOS will be presented.
- EuroQoL 5 Dimensions (EQ-5D-5L) questionnaire
  - Scores in 5 dimensions (Mobility, Self-Care, Usual Activities, Pain/Discomfort, and Anxiety/Depression) each will be presented as a frequency table and median response at baseline, 3 months, and EOS, where 1 = least impaired and 5 = most impaired. Since EQ-5D-5L is a descriptive system based on five independent dimensions, a missing answer or ambiguous answer (i.e. marking of more than one level on scale) will lead to complete rejection of the questionnaire, but the visual analog scale (VAS) score will be retained if available.
  - Overall health assessment VAS will be summarized at baseline, 3 months, and EOS. Intra-individual overall health assessment change from baseline at 3 months and EOS will be summarized.
- Work Productivity and Activity Impairment (WPAI) questionnaire scores for hemophilia effect over the last 7 days on productivity or ability at work, at school, and in regular daily activitiesiii
  - WPAI employment (Q1 = Yes)
    - Percent work time missed due to problems associated with your hemophilia:  $100 \times Q2 / (Q2 + Q4)$   
where Q2 = hours missed due to problems associated with your hemophilia and Q4 = hours actually worked.
    - Percent impairment while working due to health:  $10 \times Q5$   
where Q5 = how much did your hemophilia affect your productivity while you were working (scale is 0 to 10).
  - WPAI academic (Q5 = Yes)
    - Percent class time missed due to health:  $100 \times Q7 / Q8$   
where Q7 = hours missed due to problems associated with your hemophilia and Q8 = hours actually attended.
    - Percent impairment while attending classes due to health:  $10 \times Q9$
  - WPAI regular daily activities
    - Percent impairment of daily activities due to health:  $10 \times Q10$   
where Q10 = how much your hemophilia affected your ability to do

your regular daily activities, other than work at a job or attending classes (scale is 0 to 10)

- WPAI average impairment score is the mean of employment, academic and regular daily activities impairment scores

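### The SAP tabulates each EQ-5D-5L dimension separately and plans no index, yet one missing or ambiguous answer drops all five dimensions from the summaries

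*SAP*

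**What the plan says.** SAP 4.3.2.1 (Patient Reported Outcomes) lists the five EQ-5D-5L dimensions and says that scores "each will be presented as a frequency table and median response at baseline, 3 months, and EOS". Nothing in the SAP combines the five answers into an index, utility or profile.

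The missing-answer rule comes next. Its reason is stated first: "Since EQ-5D-5L is a descriptive system based on five independent dimensions". Its trigger is "a missing answer or ambiguous answer (i.e. marking of more than one level on scale", and its effect is that such an answer "will lead to complete rejection of the questionnaire". One exception is made: "but the visual analog scale (VAS) score will be retained if available".

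The opening of the same section adds "Missing data will not be imputed", so excluded answers are not replaced. SAP 4.3.2 places these analyses on the mITT set. SAP section 5 expects 20-25 participants to be enrolled.

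**The concern.** The reason and the rule point in opposite directions. If the dimensions are independent and summarised one at a time, a gap in Self-Care says nothing about the answer to Mobility. A complete form is needed only for a quantity that uses all five answers together, and this SAP plans none. The rule therefore takes usable answers out of the tables without protecting any planned analysis.

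What is at stake is small but avoidable: fewer observations in every dimension table at a visit, in a sample that is already small. Month 3 is the most exposed visit. EQ-5D-5L is the only questionnaire given then, so a rejected form leaves only the VAS.

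**Working it through.** The documents give no completeness figure for EQ-5D-5L, so there is no plan figure to reproduce. The check has three parts.

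**1. Loss per affected form (no assumption about frequency).** A form has 5 dimension answers. If k of them are unusable, the rule removes the 5 - k valid ones as well. For k = 1 that is 4 valid answers. In each of the other four dimensions, n falls by one at that visit:
- N = 20: 20 to 19, and 1/20 = 5%.
- N = 25: 25 to 24, and 1/25 = 4%.

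These N are expected enrolment. The mITT set may be smaller, and each loss would then weigh slightly more.

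**2. Illustration of frequency (assumed rates).** Let m be the probability that any one item is unusable, equal across items and independent between them. Then:
- Share of forms rejected = 1 - (1 - m)^5.
- Expected n per dimension under the rule = N(1 - m)^5.
- Expected n per dimension if only the affected dimension is set to missing = N(1 - m).
- Expected valid answers excluded per visit = 5N[(1 - m) - (1 - m)^5].

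| m (assumed) | Forms rejected | n per dimension, N = 20: rule / per-dimension | n per dimension, N = 25: rule / per-dimension | Valid answers excluded per visit: N = 20 (of 100) / N = 25 (of 125) |
|---|---|---|---|---|
| 1% | 4.9% | 19.0 / 19.8 | 23.8 / 24.8 | 3.9 / 4.9 |
| 2% | 9.6% | 18.1 / 19.6 | 22.6 / 24.5 | 7.6 / 9.5 |
| 5% | 22.6% | 15.5 / 19.0 | 19.3 / 23.8 | 17.6 / 22.0 |

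**3. How far the independence assumption matters.** For a given m, the rejected share cannot fall below m (all gaps on the same forms, so no valid answer is lost). It cannot exceed 5m (never two gaps on one form). The range is therefore 1% to 5% for m = 1%, 2% to 10% for m = 2%, and 5% to 25% for m = 5%. Independence lies near the upper end. If gaps cluster in the same people, the loss is smaller than the table shows.

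**The case against.** The strongest reply is that the rule may never be used. PRO data are collected in an eDiary form (SAP 4.3.2.1), and a form that forces one answer per item leaves nothing to reject. The documents do not say whether it does, so this stands as a real possibility: the loss could be nil.

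Three further replies also stand:
- The endpoint is supportive and descriptive, in a study that tests no hypothesis.
- The VAS, the one EQ-5D-5L measure for which a within-person change is specified, is kept.
- Complete-form analysis gives the same participants in all five tables at a visit, which is a tidy property, and the rule is openly pre-specified.

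None of them gives a reason to drop answers from separately reported dimensions.

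A reader might infer more than the documents support:
- **That a non-electronic route for PROs makes gaps likely.** The statement in Protocol 8.2.1 that "alternative means of diary completion will be provided" concerns the treatment and bleed diary for participants without internet access. PROs are completed in the treatment center (Protocol 8.2.2), and the alternative is not said to be non-electronic.
- **That the SAP expects double marks.** It only defines what would count as ambiguous. A contingency rule is not a forecast.
- **That the rule contradicts the haemophilia QoL scoring.** There, "Missing items will be omitted from the raw score and also from the n used to calculate range". That rule rescales a summed multi-item score, whereas EQ-5D-5L has one item per dimension and no sum in this plan. The two approaches differ but do not conflict.
- **That the answers are lost.** SAP 4.1 puts all data in the participant listings as recorded, so they leave the summaries only.
- **That 17 of 75 forms would be rejected.** The arithmetic is right (0.226 x 75 = 17.0), but it needs a 5% rate on every item, independence, and all 25 participants giving forms at all three visits.
- **That selection bias follows.** No document suggests that skipping depends on item content.

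**Conclusion.** The point holds as a minor, optional improvement. The rejection rule serves no planned analysis, its stated reason supports the opposite rule, and nothing elsewhere in the protocol or SAP limits it.

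The only size that needs no assumed missingness rate is the loss per form: up to four valid answers, and one observation fewer in each other answered dimension at that visit. The rejection percentages rest on assumed item-missing rates and on independence, and should be read as illustration rather than forecast. The true frequency is unknown and may be zero. The primary endpoint and the VAS summaries are unaffected.

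**What to change.** Replace the rejection sentence in SAP 4.3.2.1 with wording such as: *A missing or ambiguous answer is set to missing for that dimension only. All other answered dimensions and the VAS are analysed, and the number of answers is shown for each dimension and visit. All five answers are required only if an index or profile score is derived.*

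The cost is one sentence, with no new data and no change in collection. The one drawback is that denominators may differ slightly between dimensions, which the displayed n makes visible. If the eDiary form does enforce a single complete answer per item, the change has no effect on the results and does no harm.

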The EQ-5D-5L is a standardized health-related QoL questionnaire that provides a simple, generic measure of health for clinical and economic appraisal. The EQ-5D-5L descriptive system comprises 5 dimensions: mobility, self-care, usual activities, pain and discomfort, and anxiety and depression. Each dimension has 3 levels: no problems, some problems, or severe problems. The respondent is asked to indicate his/her health state by ticking (or placing a cross) in the box against the most appropriate statement in each of the 5 dimensions.

The respondent burden for the questionnaire is approximately 5 minutes.

- **Treatment Satisfaction Questionnaire for Medication (TSQM)**

The TSQM comprises 9 items across 3 domains focusing on effectiveness (3 items), convenience (3 items), and global satisfaction (3 items) of the medication over the previous 2 to 3 weeks, or since last use. All items have 5 or 7 responses, scored from one (least satisfied) to 5 or 7 (most satisfied). Item scores are summed to give 3 domain scores, which are in turn transformed to a scale of 0-100.

The respondent burden for the questionnaire is approximately 5 minutes.

- **Work Productivity and Activity Impairment (WPAI) questionnaire:**

The WPAI is a validated instrument to assess the effect of hemophilia on ability to work, attend classes, and perform regular daily activities in ages 12 and above. The WPAI will also contain classroom impairment questions. The questionnaire is self-administered and comprises 9 questions that elicit information on work, classroom, and daily activity impairment during the previous 7 days. Scores are expressed as percentages of impairment/productivity loss, with higher scores indicating greater impairment.

The respondent burden for this questionnaire is approximately 10 minutes.

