**11.2.5 Work Productivity and Activity Impairment (WPAI) Questionnaire**

**Work Productivity and Activity Impairment Questionnaire plus Classroom Impairment Questions: Hemophilia Specific (WPAI+CIQ:HS)**

The following questions ask about the effect of your hemophilia on your ability to work, attend classes, and perform regular daily activities. When you think about the past seven days, do not include today. Please check the line or fill in the blank as indicated.

1) Are you currently employed (working for pay)?

NO YES  
(If NO, check "NO" and skip to question 5.)

2) In general, how many hours per week do you usually work?

\_\_\_\_\_ HOURS

3) During the past seven days, how many hours did you miss from work because of problems associated with your hemophilia? Include hours you missed because you were sick, times you went in late, left early, etc. because you were experiencing problems with your hemophilia. (Do not include time you missed to participate in this study.)

\_\_\_\_\_ HOURS

4) During the past seven days, how much did hemophilia affect your productivity while you were working? Think about days you were limited in the amount or kind of work you could do, days you accomplished less than you would like, or days you could not do your work as carefully as usual. If hemophilia affected your work only a little, choose a low number. Choose a high number if hemophilia affected your work a great deal.

Hemophilia had no effect on my work 0 1 2 3 4 5 6 7 8 9 10

Hemophilia completely prevented me from working

CIRCLE A NUMBER

5) Do you currently attend classes in an academic setting (middle school, high school, college, graduate school, additional course work, etc.)?

NO YES  
(If NO, check "NO" and skip to question 9.)

6) In general, how many hours per week do you usually attend classes?

[figure not shown]
\_\_\_\_\_ HOURS

7) During the past seven days, how many hours did you miss from class or school because of problems associated with your hemophilia? (Do not include time you missed to participate in this study.)

[figure not shown]
\_\_\_\_\_ HOURS

8) During the past seven days, how much did hemophilia affect your productivity while in school or attending classes in an academic setting? Think about days your attention span was limited, you had trouble with comprehension or days in which you could not take tests as

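### The SAP's WPAI scoring is wrong as written, and the protocol's TSQM domain scores are dropped without being declared

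*SAP*

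**What the plan says.** **WPAI in the SAP (4.3.2.1).** Five component percentages are defined.

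- Work time missed is 100 × Q2/(Q2 + Q4), "where Q2 = hours missed due to problems associated with your hemophilia and Q4 = hours actually worked".
- Work impairment is 10 × Q5, "where Q5 = how much did your hemophilia affect your productivity while you were working (scale is 0 to 10").
- The school block then opens with "WPAI academic (Q5 = Yes").
- Class time missed is 100 × Q7/Q8, "where Q7 = hours missed due to problems associated with your hemophilia and Q8 = hours actually attended".
- Class impairment is 10 × Q9.
- Daily-activity impairment is 10 × Q10, "where Q10 = how much your hemophilia affected your ability to do" regular activities.

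The SAP version history says this scoring detail was added in version 3 for clarity.

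**WPAI in the protocol.** Section 8.2.2 states: "The questionnaire is self-administered and comprises 9 questions". The form in 11.2.5 is numbered 1 to 9. Item 2 asks "In general, how many hours per week do you usually work", and item 6 asks "In general, how many hours per week do you usually attend classes". The SAP names the instrument WPAI+CIQ:HS, which is also the title of the printed form.

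**TSQM.** Protocol 8.2.2 describes nine items in three domains of three items, each domain summed and rescaled to 0–100. SAP 4.3.2.1 gives item frequencies, medians and a single sum per participant. SAP section 1 says no protocol analysis has changed, and section 4.7 is marked not applicable.

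**The concern.** Two of the WPAI faults are visible inside the SAP alone. The class-time formula divides missed hours by attended hours, while the work-time formula a few lines earlier divides missed hours by missed plus worked hours. And Q5 cannot be both a 0–10 rating and a yes/no gate, whatever form was fielded.

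The remaining faults are disagreements with the protocol: a tenth question that does not exist there, item numbers that point to other questions, and two inputs that the printed form never asks for.

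WPAI and TSQM scores are named secondary endpoints. Enrolment starts at age 12, so the class items will apply to part of the sample. With 20–25 participants expected and means reported, one inflated value can dominate. For the TSQM, a move to less frequent dosing could raise convenience while lowering perceived effectiveness, and a single sum can cancel the two.

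**Working it through.** The plan states no figure to reproduce here. The check is an item-by-item comparison followed by evaluation of the formulas. All hours and ratings below are illustrative assumptions, because the documents give no data.

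**1. Item numbers, SAP 4.3.2.1 against the form in protocol 11.2.5**

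| SAP score | SAP item and label | Same number on the printed form | Printed item matching the label |
|---|---|---|---|
| Work time missed | Q2, hours missed | usual weekly work hours | 3 |
| Work time missed | Q4, hours worked | 0–10 work rating | none |
| Work impairment | Q5, 0–10 work rating | yes/no, attends classes | 4 |
| Class time missed | Q7, hours missed | class hours missed | 7 (agrees) |
| Class time missed | Q8, hours attended | 0–10 class rating | none |
| Class impairment | Q9 | daily-activity rating | 8 |
| Daily activity | Q10 | no such item | 9 |

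The school gate, Q5, does agree with the form. Each of the five component formulas has at least one wrong item number.

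**2. Class time missed, following the SAP's verbal labels**

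Let m be hours missed, a hours attended, and p = m/(m + a) the true share. The SAP score is m/a = p/(1 − p). For a 20-hour week:

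| m | a | SAP, 100·m/a | 100·m/(m + a) |
|---|---|---|---|
| 2 | 18 | 11.1% | 10% |
| 4 | 16 | 25% | 20% |
| 6 | 14 | 42.9% | 30% |
| 10 | 10 | 100% | 50% |
| 12 | 8 | 150% | 60% |
| 20 | 0 | undefined | 100% |

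The score is too high whenever p > 0 and passes 100% once p exceeds one half. Effect on a mean: suppose eight students, seven missing nothing and one missing 12 of 20 hours. The SAP gives 150/8 = 18.75%; the true mean is 60/8 = 7.5%.

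**3. Work time missed**

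- By label, 4 h missed and 36 h worked give 4/(4 + 36) = 10%. The structure is sound, but hours worked are not asked on the printed form.
- By literal item number on that form, 40 usual hours and a rating of 2 give 40/(40 + 2) = 95.2%. A participant with no missed hours and a rating of 0 scores 40/(40 + 0) = 100%.

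**4. TSQM**

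Seven items run 1–7 and two run 1–5, so the raw sum runs from 9 to 59. I assume items 1–3, 4–6 and 7–9 form the effectiveness, convenience and global domains, with linear rescaling. The domain spans are then 18, 18 and 14, that is 36%, 36% and 28% of the 50-point range.

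- Baseline items 6,6,6 / 4,4,4 / 4,4,6: sum 18 + 12 + 14 = 44. Domains: (18 − 3)/18 = 83.3, (12 − 3)/18 = 50.0, (14 − 3)/14 = 78.6.
- End of study 4,4,4 / 6,6,6 / 4,4,6: sum 12 + 18 + 14 = 44. Domains: 50.0, 83.3, 78.6.

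The sum shows no change, while two domains move by 33.3 points in opposite directions.

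**The case against.** The protocol calls the printed questionnaires representative examples, and the fielded form sits in an eDiary that is not available here. The SAP's numbers look like a ten-item layout, and the SAP cites an external WPAI scoring page that a programmer could consult. On this view the documents disagree, but which one is wrong is unsettled. That stands as a limit on the item-number comparison. It does not help the class-time denominator or the double use of Q5, which are wrong within the SAP, and the count of nine is in the protocol body as well as on the form. A cited page does not correct a formula that the SAP itself states.

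A second argument is that the label may be at fault rather than the denominator: if the divisor was meant to be usual class hours, missed over usual is reasonable. That is a possible repair, but it is not what the SAP says, and the printed item 8 is a rating.

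Third, a programmer following the words rather than the numbers would recover all three impairment ratings, and the 95.2% and 100% work figures need those words to be ignored. This is correct; those figures apply only to a literal reading. At 10% of class missed, the class-time error is only 1.1 points.

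Finally, on the TSQM, the protocol's analysis text asks only for descriptive statistics and change from baseline, and the SAP's item summaries would still show opposite shifts. This is why the TSQM is the lesser point. Even so, protocol 9.4.3 refers to 8.2.2 for the questionnaires, and 8.2.2 describes domain scores that the SAP never produces.

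**Conclusion.** The concern holds. Followed as written, the SAP gives a wrong class-time score: slightly high when little is missed, double the true value at one half, above 100% beyond that, and undefined at zero attendance. One item number serves two incompatible questions. Against the protocol's form, all five component formulas are mis-numbered and neither time-missed score has the inputs the SAP names. The three impairment ratings can be recovered from the verbal labels. The comparison with the form assumes that the fielded eDiary version matches the printed nine items; the denominator and Q5 faults need no such assumption.

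The missing TSQM domain scores are a smaller, undeclared departure. All of this concerns descriptive, supportive endpoints. The primary endpoint and the precision table are unaffected. It should be fixed before the analysis is programmed.

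**What to change.** 1. Reconcile every WPAI item number with the fielded eDiary form. On the printed form, work impairment is 10 × item 4, class impairment 10 × item 8, daily activity 10 × item 9, and the school gate is item 5.
2. If actual hours are collected, define both time-missed scores as 100 × missed/(missed + actual).
3. If only usual hours are collected, use 100 × item 3/item 2 for work and 100 × item 7/item 6 for class. State the usual-week assumption, and set rules for values above 100% and for zero denominators. The assumption matters: with 40 usual hours and 4 missed the score is 10%, but missed/(missed + actual) is 4/24 = 16.7% if 20 h were worked and 4/50 = 8.0% if 46 h were worked. Ten usual hours with 12 missed gives 120%.
4. For the TSQM, add the three 0–100 domain scores and state the item allocation. The split 1–3, 4–6, 7–9 is inferred from the form, since the protocol gives only three items per domain. Otherwise, declare the departure in SAP 4.7.

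The cost is SAP wording and programming. Item-level responses are collected in any case, so no new data are needed.
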